### 2.2 Rationale for combining everolimus and temozolomide in adult LGGs

There is a strong biological rationale for combining everolimus and TMZ for newly diagnosed patients with LGGs. Our collaborators at UCSF, as outlined below, have documented that TMZ treatment of LGGs in some cases appears to cause driver mutations in the PI3K/AKT/mTOR pathway that lead to malignant transformation. Therefore we believe that the addition of everolimus to TMZ will block emergence of PI3K/AKT/mTOR-activated tumor recurrence,

---

reduce the risk of TMZ-induced transformation of LGGs to higher-grade gliomas, and improve patient outcomes.

Alkylating agents such as TMZ are carcinogenic, and exposure to this class of systemic therapies is associated with a small but reproducible increased risk of developing treatment-related leukemias. In experimental systems, TMZ induces mutagenesis by methylating the O6 position of guanine, leading to mispairing with thymine. If not recognized and repaired by O6-methylguanine-DNA methyltransferase (MGMT) or by DNA mismatch repair (MMR), this results in a guanine to adenosine (G to A) transition mutation upon DNA replication. Previous analyses of recurrent GBMs have shown an association between TMZ or other alkylating agent treatment, MMR pathway mutations, and high rates of G to A mutagenesis. While MMR pathway mutations are associated with resistance to TMZ therapy, the clinical impact of TMZ-associated mutagenesis is unknown.

LGGs are slow-growing tumors that often undergo malignant transformation to an aggressive, high-grade glioma with a significantly worse prognosis. To investigate evolution of the mutational landscape over time, [name] at UCSF performed parallel sequencing of the exomes of the primary tumor, recurrent tumor, and matched normal control of 24 patients diagnosed with primary grade II astrocytomas. Six of eight patients treated with adjuvant TMZ therapy acquired more than 1,000 mutations, 95% of which were G to A, and in all six hypermutated cases, there was malignant progression to GBM. These TMZ-associated G to A mutations affected many genes linked directly to malignant phenotypes and resulted in both RB pathway deregulation and constitutive mTORC1 signaling in all six post-TMZ recurrent tumors relative to treatment naïve, patient matched primary tumors. While deregulation of these two pathways is associated with high-grade astrocytomas and has been implicated in malignant progression, the mechanisms driving these genetic changes are poorly understood. Therefore, our preliminary data suggests that TMZ therapy can drive the malignant progression of indolent grade II astrocytomas, in part through the induction of signature genetic alterations in these pathways. It is not yet clear why some but not all TMZ-exposed tumors undergo hypermutation. The somewhat predictable pattern of mutations however, suggests mTORC1 signaling is critical for malignant transformation, whether spontaneously occurring or induced by TMZ. Chronic inhibition of mTORC1 may therefore be one way to prevent or delay the initial outgrowth of malignantly transformed tumor sub-clones, and ultimately improve overall survival. Our preliminary data on the paired low-grade tumors and their high-grade recurrence support a model whereby genetic alterations that are sub-clonal can give rise to the recurrence. Thus, identification of such sub-clones at initial diagnosis is a critical step in identifying patients most likely to undergo transformation.

As malignantly transformed tumor sub-clones arise, either before or after surgical resection, initially they will be present in very few cells in the tumor, and may be undetectable by standard exome sequencing (mutation detection limit of approximately 1 in 100 cells). Thus, corresponding biomarkers of susceptibility to spontaneous or TMZ-associated malignant transformation may in fact be the alterations present in only rare cells of the initial tumor (varying degrees of sub-clonal). In a funded NIH study that will be complementary to what we propose in this clinical trial, exome sequencing of up to 2 samples per patient per surgery is

---

being used to define the frequency of TMZ induced hypermutation in a large patient cohort, including patients on this clinical trial.

In summary, these data show the direct acquisition of functionally significant driver genetic lesions in the PI3K/AKT/mTOR pathway during malignant transformation and suggest they are induced by TMZ exposure. Thus, we hypothesize that combining TMZ with everolimus will block emergence of PI3K/AKT/mTOR-activated clones and improve efficacy, as well as reduce the risk of TMZ-induced transformation of LGGs to higher-grade gliomas.

Building on the preliminary results seen in the recently-completed study of everolimus in recurrent LGGs (Haas-Kogan, Phillips et al. 2013), the proposed study will select treatment for patients both by 1p/19q chromosomal status and by whether or not their LGG demonstrates activation of the PI3K/mTOR pathway, but will target patients who have received no treatment aside from surgery, rather than potentially heavily pre-treated recurrent patients. If 1p/19q co-deletion is present, patients will be treated with single-agent everolimus. If 1p/19q co-deletion is not present but PI3K/mTOR pathway activation is present, patients will be treated with single-agent everolimus. If 1p/19q co-deletion is not present and PI3K/mTOR pathway activation is also not present, patients will be treated with a combination of everolimus and TMZ. The combination of everolimus and TMZ has been tested and found to be tolerable in GBM patients (Mason, Macneil et al. 2012) as well as in patients with melanoma (Dronca, Allred et al. 2013), as described in Section 2.4.

### **2.3 Rationale for selection by 1p/19q deletion status**

Combined 1p/19q deletion, typically involving the entire chromosome arms at both sites, is a molecular signature of oligodrogiomas, seen in 50%–80% of patients with this histology. 1p/19q co-deletion is also found in 30-50% of oligoastrocytomas and 0-15% of astrocytomas, with an overall frequency of approximately 30% in all adult LGGs [Reviewed in (Sanai, Chang et al. 2011)]. Comparative genomic hybridization, loss of heterozygosity, quantitative microsatellite analysis, and fluorescence *in situ* hybridization are all techniques used to identify tumors with 1p/19q co-deletion. The distinction between a prognostic indicator of clinical outcome regardless of therapy and a predictive measure of response to a particular therapy is very important and 1p/19q co-deletion appears to serve both roles. Its prognostic significance is reflected in longer progression-free survival and more indolent behavior in oligodrogiomas with 1p/19q co-deletion. Its predictive value is reflected in studies that first suggested that 1p/19q co-deletion is a marker of response to PCV chemotherapy and then indicated that 1p/19q co-deleted LGGs also respond favorably to temozolomide [Reviewed in (Sanai, Chang et al. 2011)]. Houillier *et al.* reported that adult LGGs exhibited an objective response rate to TMZ of 66% if 1p/19q co-deletion was present but only 31% if 1p/19q co-deletion was absent (Houillier, Wang et al. 2010). Because of its role as a prognostic factor and predictive marker, paradigms for treatment of adult LGGs incorporate 1p/19q co-deletion status into the decision making process. Therefore, in our study of everolimus for newly diagnosed adult LGGs for whom treatment will be selected by activation of the PI3K/mTOR pathway, we have also chosen to select treatment based on patients' tumor 1p/19q co-deletion status. On this clinical trial, favorable patient with 1p/19q co-deletion will receive single agent everolimus.

---

The less favorable group that lacks 1p/19q co-deletion will be further selected by PI3K/mTOR pathway activation, with pathway activated tumors (reflected in positive phospho-PRAS40 staining) receiving single agent everolimus and pathway non-activated tumors (reflected in negative phospho-PRAS40 staining) receiving dual therapy with everolimus and temozolomide.

In contrast to oligodendrogiomas and oligoastrocytomas there is a high incidence of somatic mutations in the alpha thalassemia/mental retardation syndrome X-linked (ATRX) gene in diffuse astrocytomas with mutation in IDH1/IDH2 (Jio 2012; Kannan K 2012; Killela PJ 2013]. Based on our current understanding of diffuse glioma, in the vast majority of cases ATRX mutation is mutually exclusive with 1p/19q-coeletion and mutually exclusive with TERT promoter mutation, and several studies now demonstrate that ATRX mutation status can be used in combination with IDH1/IDH2 mutation status and 1p/19q-codeletion status to generate a molecular diagnostic algorithm that is superior to histopathologic classification alone to identify patient subgroups with different outcomes (Wiestler B 2013; Reuss DE et al. 2014; Cancer Genome Atlas Research Network 2015; Eckel-Passow JE 2015). Thus, low-grade tumors with mutation in ATRX will lack 1p/19q-codeletion and low-grade tumors without ATRX mutation will have 1p/19q-codeletion.

## 2.4 Safety of combined everolimus and temozolomide

The combination of everolimus and temozolomide has been reported in a phase I study (Mason, Macneil, et al., 2012) combining the two drugs for treatment of GBM, either in the adjuvant setting immediately after radiation or in the setting of first recurrence after initial treatment, as well as in a phase II study in patients with metastatic, unresectable melanoma (Dronca, Allred, et al, 2013). In the phase I study, the recommended phase II dose was everolimus 10 mg/day with TMZ 150 mg/m^2/d x 5 days out of 28. At this dose, myelosuppression was mild, with 2 patients each having grade 3 thrombocytopenia, lymphopenia, and granulocytopenia. Common adverse events otherwise included mild fatigue, flushing, pruritus, rash, mucositis, nausea and vomiting, headache, cough and mild pneumonitis. The combination of everolimus and TMZ at 200 mg/m^2/d was attempted only in combination with an everolimus dose of 2.5 mg/day; this dose level had no DLTs, but 3 of 4 patients required a delay in restarting TMZ, and 2 of 3 patients were dose-reduced to TMZ 150 mg/m^2/d, so no further attempts to treat patients at 200 mg/m^2/d were made in that study. In the phase II study in melanoma patients, patients were treated with everolimus 10 mg/d 5 days/week, with TMZ dosed at 200 mg/m^2/d x 5 days out of 28. 9 out of 48 patients required dose reduction due to myelotoxicity, but overall the combination was well-tolerated, with the most common other toxicities being fatigue, nausea and elevated liver enzymes.

Given this clinical experience with the combination of everolimus and TMZ, we will treat patients at 10 mg daily of everolimus and 150 mg/m^2/d x 5 days out of 28 for the first cycle. If the first cycle is well-tolerated, the treating physician will have the option to increase TMZ to 200 mg/m^2/d for the second cycle and beyond.

### 3 Objectives and endpoints

#### Objectives:

##### **Primary objectives**

**Arm 1:** To assess progression-free survival in patients with previously untreated ATRX lost and/or 1p/19q intact, PI3K/mTOR pathway-activated LGG treated with everolimus.

**Arm 2:** To assess progression-free survival in patients with previously untreated ATRX lost and/or 1p/19q intact, PI3K/mTOR pathway-non-activated LGG treated with everolimus and TMZ.

**Arm 3:** To assess progression-free survival in patients with previously untreated ATRX intact and/or 1p/19q co-deleted LGG treated with everolimus.

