#### Inclusion criteria:

1. Age  $\geq$  18 years
2. KPS  $\geq$  60
3. Adequate bone marrow function as shown by: ANC  $\geq$  1.5  $\times$  10^9/L, Platelets  $\geq$  100  $\times$  10^9/L, Hb  $\geq$  9.0 g/dL;
4. Adequate liver function as shown by:
  - a. Total serum bilirubin  $\leq$  2.0 mg/dL,

- b. ALT and AST  $\leq$  2.5x ULN,
- c. INR  $\leq$  2;
- 5. Adequate renal function: serum creatinine  $\leq$  1.5 x ULN;
- 6. Fasting serum cholesterol  $\leq$  300 mg/dL OR  $\leq$  7.75 mmol/L AND fasting triglycerides  $\leq$  2.5x ULN. NOTE: In case one or both of these thresholds are exceeded, the patient can only be included after initiation of appropriate lipid lowering medication with confirmed reduction of lab values to within eligibility parameters;
- 7. Signed informed consent obtained prior to any screening procedures.
- 8. Patients must have histologically proven supratentorial low-grade glioma at initial diagnosis and at the time of any subsequent surgeries; pathology must have been reviewed by UCSF neuropathology. Eligible low-grade gliomas include: astrocytoma, oligodendrogloma and mixed oligoastrocytoma. Pilocytic astrocytomas are excluded.
- 9. Patient's tumor must have documentation of the presence of an IDH-1 and/or IDH-2 mutation of any type.
- 10. Results of ATRX and/or 1p/19q chromosomal status: if ATRX is lost, 1p/19q status is not required. If ATRX is intact, 1p/19q chromosomal status must be available to permit treatment selection.
- 11. Results of pRAS40 testing.
- 12. Patients must have evaluable disease. Patients must begin treatment within 120 days of most recent surgical procedure.

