#### 6.1.3 Treatment assignment

Patient treatment will be selected by whether or not their tumor tissue demonstrates 1p/19q chromosomal co-deletion and by PI3K/mTOR pathway activation (see Section 7.3.2). As per Section 4, patients whose tumors are ATRX lost and/or 1p/19q intact and that demonstrate pathway activation will be treated on Arm 1 with single-agent everolimus. Patients whose tumors are ATRX lost and/or 1p/19q intact but do not demonstrate pathway activation will be treated on Arm 2 with the combination of everolimus and temozolomide. Patients whose tumors are 1p/19q co-deleted will be treated on Arm 3 with single-agent everolimus regardless of mTOR pathway status. Patients whose tumors are ATRX intact must be tested for 1p/19q

---

co-deletion and, if co-deletion is confirmed they will be treated on Arm 3 with single-agent everolimus regardless of mTOR pathway status.

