## 9.3 Determination of Sample Size and Accrual Rate

Documentation of prognosis among LGG patients treated with TMZ is limited in the published literature. A recent study was conducted to assess whether IDH1 or IDH2 mutations predict longer survival in LGG patients (Houillier, Wang et al. 2010). In this study, it was reported that the median PFS among LGG patients whose tumors were 1p-19q co-deleted and IDH mutated was 37.9 months while it was 32.9 months for the patients whose tumors were 1p-19q intact and IDH mutated.

**Arm 1:** As we expect patients with LGGs that are IDH-mutated with ATRX loss and/or 1p/19q chromosomes intact, and with PI3K/mTOR pathway activated (Pathact) treated with everolimus to have better prognosis than if treated with TMZ alone, we consider the lower threshold for the probability of 33-month PFS to be 50%. If the true PFS-33 proportion is 70%, with 35 patients we will have 86% confidence in the PFS-33 estimate with a one-tailed 90% confidence interval.

**Arm 2:** Similarly, we expect patients with LGGs that are IDH-mutated with ATRX loss and/or 1p/19q chromosomes intact, and with PI3K/mTOR pathway non-activated (Pathnon-act) treated with the combination of everolimus and TMZ to have better prognosis than if treated solely with TMZ, we again consider the lower threshold for the probability of 33-month PFS to be 50%. If the true PFS-33 proportion is 70%, with 35 patients we will have 86% confidence in the PFS-33 estimate with a one-tailed 90% confidence interval.

**Arm 3:** We expect patients with ATRX intact and/or 1p-19q co-deleted (regardless of PI3K/mTOR pathway status) LGGs treated with everolimus to have better prognosis than if treated with TMZ alone. Therefore, we consider the lower threshold for the probability of 38-month PFS to be 50%. If the true PFS-38 proportion is 70%, with 35 patients we will have 86% confidence in the PFS-38 estimate with a one-tailed 90% confidence interval.

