All tumor tissues will be analyzed to assess both 1p/19q chromosomal status and activation of PI3K/Akt/mTOR signaling. 1p/19q chromosomal status will be performed and interpreted in a laboratory which is CAP accredited and CLIA certified to perform high complexity testing. The 1p/19q Deletion by FISH assay is designed to identify chromosomal deletions involving the 1p36 and 19q13 regions. It utilizes two Vysis(TM) dual-color DNA probe sets. Probe set one includes the loci-specific identifier (LSI) 1p36 that hybridizes to the 1p target on chromosome 1, producing an orange signal while LSI 1q25 serves as a reference probe for 1q, producing a green signal. Likewise, probe set two includes LSI 19q13 that hybridizes to the 19q target on chromosome 19, producing an orange signal, and a 19p reference probe LSI 19p13 that produces a green signal. Formalin-fixed, paraffin-embedded tissue on two glass slides is de-paraffinized and then treated with pepsin to digest tissue proteins and allow for probes to reach target DNA. The DNA is then heat denatured and subsequently allowed to hybridize with the two probe sets, one per slide. After hybridization, the slides are washed to remove any of the excess unbound probes and the nuclei are counterstained with DAPI (4,6 diamidino-2-phenylidole). Enumeration of 1p, 1q, 19p and 19q signals is conducted by

microscopic examination of cell nuclei using a fluorescence microscope equipped with appropriate excitation and emission filters. An adjacent H&E stained section of the case is reviewed to evaluate tumor and normal tissue morphology and to identify the appropriate area of FISH analysis.

In addition, all tumors will be molecularly profiled based on known alterations in adult LGGs. First, tumors will be divided into one of two categories, PI3K/AKT/mTOR activated (Pathact) or non-activated (Pathnon-act), based upon the results of immunohistochemistry (IHC) for p-PRAS40 as described below. Second, all tumor samples will be further characterized by IHC, tumor-DNA sequencing, and FISH, for additional molecular aberrations, as described below.

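### ATRX-lost, 1p/19q-co-deleted tumors are assigned to two different arms, and the and/or population wording in Sections 3 and 9.3 also overlaps for ATRX-intact, 1p/19q-intact tumors

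*Combined protocol and SAP*

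**What the plan says.** Section 3 gives the Arm 1 population as "previously untreated ATRX lost and/or 1p/19q intact, PI3K/mTOR pathway-activated LGG treated with everolimus", Arm 2 as "previously untreated ATRX lost and/or 1p/19q intact, PI3K/mTOR pathway-non-activated LGG treated with everolimus and TMZ" and Arm 3 as "previously untreated ATRX intact and/or 1p/19q co-deleted LGG treated with everolimus". Section 9.3 repeats the pattern; for Arm 3 it reads "We expect patients with ATRX intact and/or 1p-19q co-deleted (regardless of PI3K/mTOR pathway status) LGGs treated with everolimus".

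The assignment rules are spread over several sections:

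- **Section 6.1.3** says that "patients whose tumors are ATRX lost and/or 1p/19q intact and that demonstrate pathway activation will be treated on Arm 1 with single-agent everolimus", with the parallel rule for Arm 2 when the pathway is not activated. It then says: "Patients whose tumors are 1p/19q co-deleted will be treated on Arm 3 with single-agent everolimus regardless of mTOR pathway status". ATRX-intact tumors must be tested for 1p/19q and enter Arm 3 if co-deletion is confirmed.
- **Section 4** sends any tumor that is ATRX-lost or 1p/19q-intact to the pathway split (Arm 1 or 2). Its route to Arm 3 needs either ATRX intact with co-deletion confirmed, or 1p/19q as the only result at hand.
- **Sections 2.2 and 2.3** give single-agent everolimus to co-deleted tumors and apply the pathway split only to those without co-deletion. **Section 7.3.2** likewise applies the split to 1p/19q-intact tumors.
- **Inclusion criterion 10 (Section 5.1)** requires 1p/19q status when ATRX is intact, but "if ATRX is lost, 1p/19q status is not required". **Appendix 2, Section A** states: "All tumor tissues will be analyzed to assess both 1p/19q chromosomal status and activation of PI3K/Akt/mTOR signaling".

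The landmark is 33 months in Arms 1 and 2 and 38 months in Arm 3. The historical medians behind them, in Section 9.3, are defined by 1p/19q status: 32.9 months (intact) and 37.9 months (co-deleted).

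**The concern.** Two markers classify the tumors, and the arm definitions join them by and/or. That is safe only if the markers never disagree. Section 2.3 says that ATRX mutation and co-deletion exclude each other in most tumors, not in all, and then concludes as though the rule were absolute.

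For a tumor that breaks the rule, the arm decides three things: the analysis set, the landmark at which success is judged, and in some cases whether temozolomide is part of the regimen. If two sections give different arms and neither prevails, the choice is made case by case, and the primary-analysis populations are not fixed in advance.

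**Working it through.** **1. Each marker combination against each rule.**

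| Tumor | Sections 3 and 9.3 | Section 4 | Section 6.1.3 | Sections 2.2, 2.3, 7.3.2 |
|---|---|---|---|---|
| ATRX lost, 1p/19q intact | 1/2 | 1/2 | 1/2 | pathway split |
| ATRX lost, co-deleted | 1/2 and 3 | 1/2 | 1/2 and 3 | single-agent everolimus, no pathway split |
| ATRX intact, 1p/19q intact | 1/2 and 3 | 1/2 | 1/2 | pathway split |
| ATRX intact, co-deleted | 3 | 3 | 3 | single-agent everolimus, no pathway split |
| ATRX lost, 1p/19q not tested | 1/2 | 1/2 | 1/2 | not settled |
| Only 1p/19q available, co-deleted | 3 | 3 | 3 | single-agent everolimus, no pathway split |

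The second row is a contradiction in the assignment rules themselves. In the third row only the population wording overlaps, because every operational rule gives Arms 1/2.

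**2. What differs for an ATRX-lost, co-deleted tumor.**

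- Pathway non-activated: Arm 2 (everolimus plus temozolomide, 33 months) or Arm 3 (everolimus alone, 38 months). Regimen, analysis arm and landmark all differ.
- Pathway activated: Arm 1 or Arm 3. The regimen is the same, single-agent everolimus. Only the analysis arm and landmark differ.

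Section 7.3.2 expects about 50% of tumors to be activated whatever the 1p/19q status, so the regimen would differ for roughly half of such patients.

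**3. The plan's own figure.** Section 9.3 uses 35 patients per arm, a lower threshold of 50%, a true value of 70% and a one-tailed 90% interval, and states 86%. Treat the landmark as a binary outcome known for everyone. The smallest count with one-sided error at most 0.10 is then 22 of 35 (exact one-sided 90% lower bound 0.506):

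- P(X ≥ 22 | 35, 0.50) = 0.0877
- P(X ≥ 22 | 35, 0.70) = 0.8650

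The 86% reproduces, read as power.

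**4. Effect of placing such patients in Arm 1 or 2.** With exponential PFS, S(t) = 0.5^(t/median).

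- 1p/19q intact at 33 months: 0.5^(33/32.9) = 0.499, which is the plan's 50%.
- Co-deleted at 33 months: 0.5^(33/37.9) = 0.547.

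If a fraction q of the arm is co-deleted, the null becomes (1 − q) × 0.50 + q × 0.547. The documents give no value for q, so the values below are assumptions.

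| q | Patients of 35 | Null PFS-33 | P(X ≥ 22) |
|---|---|---|---|
| 0 | 0 | 0.500 | 0.088 |
| 5% | 1.75 | 0.502 | 0.092 |
| 10% | 3.5 | 0.505 | 0.097 |
| 20% | 7 | 0.509 | 0.107 |

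The 20% row is an extreme that sits badly with Section 2.3. If the same patients go to Arm 3, they match its co-deleted benchmark and its null does not move.

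**The case against.** The strongest defence is that Section 4, taken alone, gives every tested combination exactly one branch, and Section 6.1.3 says that it follows Section 4. On that view and/or only reflects which test was available, and an ATRX-lost tumor goes to the pathway split. A co-deletion might not even be known at assignment: criterion 10 does not ask for 1p/19q when ATRX is lost, and Appendix 2, which is cited under the correlative studies, gives no timing. Under intention to treat (Section 9.5), a later result would not move the patient.

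Much of this stands. Section 4 does not overlap, early detection is not established, and the numerical effect is small. It does not remove the conflict. The co-deleted sentence in Section 6.1.3 carries no exception for ATRX loss, Sections 2.2, 2.3 and 7.3.2 support it, and nothing says that Section 4 prevails. Intention to treat presupposes one assigned arm.

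A reader might go further and infer that ATRX-intact, 1p/19q-intact tumors also have an ambiguous treatment and could dilute Arm 3. The documents do not support that. Criterion 10 requires their 1p/19q result, Sections 4 and 6.1.3 admit ATRX-intact tumors to Arm 3 only with confirmed co-deletion, and Sections 4, 6.1.3 and 7.3.2 send 1p/19q-intact tumors to the pathway split.

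**Conclusion.** Wrong as written, with a small effect. For ATRX-lost, co-deleted tumors the assignment text contradicts itself within Section 6.1.3 and across sections. Analysis arm and landmark are undetermined, and so is the regimen when the pathway is non-activated. For ATRX-intact, 1p/19q-intact tumors only the population wording in Sections 3 and 9.3 needs correcting.

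If an assumed 5-10% of Arm 1 or 2 were co-deleted, the exact one-sided error rate would move from 0.088 to about 0.092-0.097. This rests on exponential PFS, the plan's historical medians, and a binary landmark with complete follow-up. The 35 patients per arm and the power of 0.865 at a true 70% are unchanged.

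Two further inferences would go too far. The number of affected patients cannot be estimated, because no discordance rate is given. Nor does the regimen differ for every affected patient, since Arms 1 and 3 give the same treatment.

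**What to change.** Replace the and/or wording with one mutually exclusive assignment table, and use it unchanged in Sections 3, 4, 6.1.3, 7.3.2 and 9.3, with criterion 10 and the rationale in Sections 2.2 and 2.3 brought into line. The table should cover the four ATRX by 1p/19q cells and the untested states that the protocol permits: ATRX lost with 1p/19q unknown, and only 1p/19q available. State that a 1p/19q result arriving after assignment does not change the analysis arm. Which arm each discordant cell enters is for the investigators to decide.

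The cost is a wording amendment with the usual approvals. It rises only if the chosen rule needs 1p/19q status in ATRX-lost tumors before assignment, because criterion 10 and the screening tests would then have to change as well. No sample-size recalculation is needed.
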